10.1.2 Duration of exposure and time at risk in the Maintenance Period

- The study medication duration during the Maintenance Period will be calculated as follows:

$$\text{Date of last dose (MP)} - \text{Date of first dose (MP)} + 28$$

- If date of last dose in the Maintenance Period + 28 days extends to a date beyond the final visit date of the Maintenance Period (not including SFU), then this calculation reverts to:

$$\text{Date of last visit (MP - not including SFU)} - \text{Date of first dose (MP)} + 1$$

- For study participants who die during the Maintenance Period, then this calculation reverts to:

$$\text{Date of death} - \text{Date of first dose (MP)} + 1$$

- For study participants who discontinue/lost to follow-up during the Maintenance Period, then this calculation reverts to:

$$\text{Date of last dose (MP)} - \text{Date of first dose (MP)} + 28$$

- The time at risk during the Maintenance Period will be calculated as follows:

- For study participants who complete the Maintenance Period as planned and continue into an open-label study (and, therefore, do not have the SFU visit in the feeder study):

$$\text{Date of last visit (MP)} - \text{Date of first dose (MP)} + 1$$

- For study participants who die during the Maintenance Period, then this calculation reverts to:

$$\text{Date of death} - \text{Date of first dose (MP)} + 1$$

- For all other study participants, use the minimum of the following:

- $$\text{Date of last dose (MP)} - \text{Date of first dose (MP)} + 140 + 1$$
 - $$\text{Date of last clinical contact} - \text{Date of first dose (MP)} + 1$$

This last group could include study participants who discontinue the Maintenance Period early, study participants who complete the Maintenance Period as scheduled but choose not to continue into an open-label study, or study participants who are ongoing in the SFU period at the time of the interim data snapshot.

Note that the Week 24 visit (ie, Visit 10) will be the last visit for the Week 24 interim analysis, and that the Week 52 visit (ie, Visit 17) will be the last visit for the Week 52 interim analysis.

10.1.3 Duration of exposure and time at risk in the combined Double-Blind Treatment and Maintenance Periods

- The study medication duration during the combined treatment period will be calculated as follows:

- For study participants who do not switch study treatments per study design:

$$\text{Date of last dose} - \text{Date of first dose} + 28$$

- If the date of last dose + 28 days extends to a date beyond the date of the final visit date (not including SFU), then this calculation reverts to:

$$\text{Date of last visit (not including SFU)} - \text{Date of first dose} + 1$$

- For study participants who die, then this calculation reverts to:

$$\text{Date of death} - \text{Date of first dose} + 1$$

- For study participants who switch study treatments per study design (ie, study participants initially randomized to placebo who are re-allocated to bimekizumab treatment):

- During the DBTP (attributed to initially randomized treatment):

$$\text{Date of last dose (DBTP)} - \text{Date of first dose (DBTP)} + 28$$

Note: If date of last dose in the Initial Period + 28 days extends to a date beyond the date of first dose in the Maintenance Period, then this calculation reverts to:

$$\text{Date of first dose (MP)} - \text{Date of first dose (DBTP)} + 1$$

- During the Maintenance Period (attributed to the treatment initiated in the Maintenance Period), the study medication duration algorithm specified for the Maintenance Period in Section 10.1.2 applies.

- Definitions for time at risk during the combined treatment period will be calculated as follows:

- For study participants who do not switch study treatments per study design:

- For study participants who complete the Maintenance Period as planned and continue into an open-label study (and, therefore, do not have the SFU visit in the feeder study):

$$\text{Date of last visit} - \text{Date of first dose} + 1$$

- For study participants who die prior to the final visit:

$$\text{Date of death} - \text{Date of first dose} + 1$$

- For all other study participants, use the minimum of the following:
 - $Date of last dose - Date of first dose + 140 + 1$
 - $Date of last clinical contact - Date of first dose + 1$

This last group could include study participants who discontinue early, study participants who complete the Maintenance Period as scheduled but choose not to continue into an open-label study, or study participants who are ongoing in the SFU period at the time of the data snapshot.

- For study participants who switch study treatments per study design:

- During the DBTP (attributed to initially randomized treatment):

$$Date of first dose (MP) - 1 - Date of first dose (DPTB) + 1$$

This assumes that any study participant in this category has completed the DBTP and doses [with a new study treatment] in the Maintenance Period.

- During the Maintenance Period (attributed to the treatment initiated in the Maintenance Period), the time at risk algorithm specified for the Maintenance Period in Section 10.1.2 applies.

Note that the Week 24 visit (ie, Visit 10) will be the last visit for the Week 24 interim analysis, and Week 52 visit (ie, Visit 17) will be the last visit for the Week 52 interim analysis.

In addition, Week 20 visit will correspond to the last dose of the Week 24 interim analysis. and the Week 48 visit will correspond to the last dose of the Week 52 interim analysis.

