4.3 Interim analysis and data monitoring

4.3.1 Interim analyses

Two interim analyses will be conducted:

- The first interim analysis will be conducted after the planned number of randomized study participants have completed the Double-Blind Treatment Period and the 24 week assessments or have withdrawn from IMP or the study. The purpose of this analysis is to prepare a regulatory submission for a Marketing Authorization Application based on this analysis.
- The second interim analysis will be conducted after the planned number of study participants have completed Week 52 or have withdrawn from IMP or the study. The purpose of this second interim analysis is to perform a comprehensive evaluation of all available data for the study and to supplement the regulatory submission based on the Week 24 interim analysis.

The database for the Week 24 interim analysis will include all available data collected up to the day the last planned study participant completed the Week 24 Visit (even if this study participant has withdrawn from IMP). Study participants who discontinued the study prior to Week 24 will be included in this first interim analysis.

The Week 24 interim analysis will evaluate the primary, secondary and other efficacy variables, as well as the safety and PK/immunogenicity variable results. The disposition, demographics and other Baseline characteristics, protocol deviations and compliance will also be described.

The efficacy analyses will present data until Week 24, and the safety analyses will include all available data collected up to the day the last planned study participant completed the Week 24 Visit. This may include safety data beyond the Week 24 timepoint. Events on-going at the time of the interim analysis (eg, concomitant medications, or adverse events) will be analyzed as they are collected to date (ie, up to Week 24 of last participant for safety endpoints), and analyses based on these events will be revised at time of the second interim analysis and/or final analysis.

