Tables/graph on time to ASAS response	RS (DB-period only)	
 • Placebo • BKZ 160mg Q4W 	Yes, for all visits up to Week 16 for each participant	Yes, rerun of analyses provided for interim analysis 1
By-visit tables	RS	
 • Placebo • BKZ 160mg Q4W 	Yes, for all visits up to Week 24 for each participant	Yes, for all visits up to Week 52 for each participant
Safety Variables				
Tables of adverse events	SS (DB-period only)	
 • Placebo • BKZ 160mg Q4W 	Yes, for all visits up to Week 16 for each participant	No
	MS (MP only)	
 • BKZ 160mg Q4W Total 	No	Yes, from Week 16 up to Week 52 for each participant
	SS (Overall period)	
 • BKZ 160mg Q4W Total 	Yes, for all visits up to date of Week 24 visit of last planned participant	Yes, for all visits up to date of Week 52 visit of last planned participant
By-visit tables on laboratory or VS data	SS (Overall period)	
 • Placebo / BKZ 160mg Q4W • BKZ 160mg Q4W 	Yes, for all visits up to date of Week 24 visit of last planned participant	Yes, for all visits up to date of Week 52 visit of last planned participant

Variable	Analysis Sets (study period)	Treatment groups	Interim Analysis 1	Interim Analysis 2
Type of tables Shift table or table on TEMA for laboratory data or Hy's Law cases	SS (DB-period only)	
 Placebo BKZ 160mg Q4W 	Yes, for all visits up to Week 16 for each participant	No
	MS ^a (MP only)	
 BKZ 160mg Q4W Total 	No	Yes, from Week 16 up to Week 52
	SS ^a (Overall period)	
 BKZ 160mg Q4W Total 	Yes, for all visits up to date of Week 24 visit of last planned participant	Yes, for all visits up to date of Week 52 visit of last planned participant
Table on TEMA for VS data	SS (DB-period only)	
 Placebo BKZ 160mg Q4W 	Yes, for all visits up to Week 16 for each participant	No
	MS ^a (MP only)	
 BKZ 160mg Q4W Total 	No	Yes, from Week 16 up to Week 52 for each participant
	SS ^a (Overall period)	
 BKZ 160mg Q4W Total 	Yes, for all visits up to date of Week 24 visit of last planned participant	Yes, for all visits up to date of Week 52 visit of last planned participant

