10.1 Extent of exposure

Two summary tables will be created to describe the extent of exposure.

The first table consists of a descriptive summary of study medication duration (in days), total study medication duration in (subject-years), and total time at risk (in subject-years). The information will be presented overall (ie, for the entire treatment period (Double-Blind Treatment Period (DBTP) and Maintenance Period (MP) combined)) as well as by treatment periods.

Study medication duration in subject-years is obtained as study medication in days divided by 365.25. Similarly, total time at risk in subject-years is obtained as total time at risk in days divided by 365.25.

A second summary will be created on the cumulative study medication duration for the overall period, as well as by treatment periods.

- The following time durations categories will be considered for the overall period: ≥ 0 weeks, ≥ 16 weeks, ≥ 24 weeks, ≥ 48 weeks.
- The following time durations categories will be considered for the Double-Blind Treatment Period: ≥ 0 weeks, ≥ 4 weeks, ≥ 8 weeks, ≥ 12 weeks.
- The following time durations categories will be considered for the Maintenance Period: ≥ 0 weeks, ≥ 16 weeks, ≥ 24 weeks, ≥ 36 weeks.

A by-study participant listing of date of first and last dose and the duration of exposure will be performed.

The study medication duration (in days) and the time at risk (in days) are defined depending on the study period of interest. See Section 10.1.1 to Section 10.1.5 for further details.

Throughout this section, date of last clinical contact for each study participant is defined as the maximum of [last visit date including SFU visit, last AE start date (including imputed AE start dates), date of study termination or completion, last date of study drug administration].

10.1.1 Duration of exposure and time at risk in the Double-Blind Treatment Period (DBTP)

- The study medication duration during the DBTP will be calculated as follows:

$$\text{Date of last dose (DBTP)} - \text{Date of first dose (DBTP)} + 28$$

(this formula also applies for study participants who discontinue/lost to follow-up during the DBTP).

- If the date of last dose of the DBTP + 28 days extends to a date beyond the date of first dose of the Maintenance period, then this calculation reverts to:

$$\text{Date of first dose (MP)} - \text{Date of first dose (DBTP)} + 1$$

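### At the Week 24 interim, overall-period adverse events run to the data cut-off, but the notes under the time-at-risk rules stop follow-up at Week 24 unless a later adverse event extends it

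*SAP*

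**What the plan says.** **Events counted.** For the first interim, SAP Section 4.3.1 states that "the safety analyses will include all available data collected up to the day the last planned study participant completed the Week 24 Visit", and adds: "This may include safety data beyond the Week 24 timepoint". Table 4-3 gives the same limit for the overall-period adverse event tables (Safety Set, BKZ Total column): "Yes, for all visits up to date of Week 24 visit of last planned participant".

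**Time at risk.** For bimekizumab-randomized participants who neither died nor rolled over to the open-label study, Section 10.1.3 takes the smaller of two quantities. One is "Date of last dose - Date of first dose + 140 + 1"; the other is last clinical contact minus first dose plus 1. Section 10.1.2 has the parallel rule for placebo participants after the switch. Section 10.1 defines last clinical contact as the latest of four dates: last visit, "last AE start date (including imputed AE start dates"), study termination or completion, and last drug administration.

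**The notes.** Sections 10.1.2 and 10.1.3 both end with: "Note that the Week 24 visit (ie, Visit 10) will be the last visit for the Week 24 interim analysis". Section 10.1.3 adds: "In addition, Week 20 visit will correspond to the last dose of the Week 24 interim analysis". The same sentences pair Week 52 and Week 48 with the second interim.

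**Use.** Section 10.2 makes total time at risk the EAER denominator, and uses time at risk as the EAIR contribution of participants without the event. Section 4.3.1 says of the first interim: "The purpose of this analysis is to prepare a regulatory submission for a Marketing Authorization Application based on this analysis".

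**The concern.** The numerator follows a calendar cut-off and the denominator, on the wording of the notes, follows a study week. Someone enrolled a year before the last participant is near Week 52 at the cut-off. Their later adverse events are counted, while their event-free time after Week 24 is not.

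The denominator also responds to the outcome. Once the notes fix the last visit and last dose, the remaining way for an ongoing participant to gain person-time after Week 24 is to have an adverse event there. Two participants followed equally long receive different time at risk because one had an event.

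The rates per 100 subject-years in the submission analysis are at stake. The overall-period tables show only the BKZ Total column, so no concurrent control column would reveal the shift, and the rates would not be comparable with correctly aligned rates from later analyses.

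**Working it through.** The SAP states no exposure total or adverse event rate, so there is no figure to reproduce. The check applies its rules.

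**Inputs from the SAP.** 200 bimekizumab and 100 placebo participants, the latter switching at Week 16 (day 112); last dose day 140 and last visit day 168 under the notes.

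**Assumptions not in the SAP.** Uniform accrual over A = 13, 26, 52 or 78 weeks, no dropout, follow-up capped at Week 52, and a constant rate of 0.5 to 4 adverse events per subject-year.

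**Step 1: an ongoing participant with no later event, notes as written.**
- Bimekizumab-randomized: dose limit 140 + 140 + 1 = 281 days; contact limit 168 + 1 = 169 days; time at risk 169 days.
- Placebo switcher: dose limit (140 − 112) + 141 = 169 days; contact limit (168 − 112) + 1 = 57 days; time at risk 57 days.

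The Week 24 visit is the binding limit. The Week 20 dose plus 140 days reaches day 280, which is Week 40. The Week 20 note mainly truncates study medication duration, to 140 + 28 = 168 days whatever was actually given.

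**Step 2: total if nobody is extended.** (200 × 169 + 100 × 57) / 365.25 = 39,500 / 365.25 = 108.1 subject-years.

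**Step 3: follow-up to the cut-off.** Extra follow-up per participant is min(U, 28) weeks, with U uniform on 0 to A. Its mean is A/2 for A up to 28, otherwise (28²/2 + 28 × (A − 28)) / A. This gives 6.5, 13, 20.5 and 23.0 weeks. For A = 26, the added time is 300 × 13 × 7 / 365.25 = 74.7 subject-years, so the total is 108.1 + 74.7, about 183.

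**Step 4: the rule as written.** By simulation, a later adverse event start extends last clinical contact, up to the dose limit. Inflation is subject-years to the cut-off divided by subject-years under the rule.

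| Accrual (weeks) | Subject-years to cut-off | Under the rule, 0.5 to 4 events per subject-year | EAER inflation |
|---|---|---|---|
| 13 | 145 | 110 to 118 | 1.32 to 1.23 |
| 26 | 183 | 114 to 138 | 1.61 to 1.32 |
| 52 | 226 | 119 to 159 | 1.90 to 1.42 |
| 78 | 240 | 121 to 165 | 1.99 to 1.45 |

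The EAIR for an event occurring at 5 per 100 subject-years shows almost the same ratios.

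**Step 5: the benign reading.** Suppose the notes only name milestones and actual 4-weekly visits and doses feed last clinical contact. For A = 26, 52 and 78, time at risk is about 171, 219 and 235 subject-years, against 182, 225 and 239 to the cut-off (leaving out the one-day increments). The ratios are 182/171 = 1.06, 225/219 = 1.03 and 239/235 = 1.02.

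**The case against.** The strongest reply is that the notes do not truncate anything. Week 24 with Week 20, and Week 52 with Week 48, are the scheduled last visit and dose of each milestone. The operative definition of last clinical contact uses dates in the database, which runs to the cut-off. Sections 10.1.2 and 10.1.3 also provide for participants who have completed maintenance or are in safety follow-up at the snapshot, which sits badly with a Week 24 cap. This reading is tenable, and under it the discrepancy falls to a few percent. It does not remove the point. The notes stand directly under the formulas, nothing states that actual dates override them, and the listed examples of the residual group do not mention participants still being dosed. Two programmers could derive materially different rates. Even with actual dates, an event after the last visit extends time at risk while event-free time there is lost.

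A reader might infer three stronger things that the SAP does not support.
- *Time at risk closes at Week 24 for everyone, inflating rates up to 2.2 times (240/108).* The definition of last clinical contact includes the last adverse event start, so strict closure is not what is prescribed.
- *The Week 20 dose shortens time at risk.* Its 140-day extension reaches Week 40; the Week 24 visit binds first.
- *The safety comparison with placebo is distorted.* The double-blind tables have their own time-at-risk rule in Section 10.1.1, and the risk differences in Section 10.2.2 use crude proportions. Percentages and event counts do not use time at risk.

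It is also fair to say that the error runs against bimekizumab and that safety summaries are rerun at the final analysis.

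**Conclusion.** The conflict between Section 4.3.1 with Table 4-3 and the notes in Sections 10.1.2 and 10.1.3 is real, and nothing else in the SAP resolves it. It affects only the overall-period exposure-adjusted rates for bimekizumab and the study medication duration at this interim.

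With the notes applied as written, EAIR and EAER are overstated by about 1.2 to 2.0 times. That range rests on the assumed accrual of 13 to 78 weeks, no dropout and 0.5 to 4 adverse events per subject-year; the true size depends on an accrual pattern the SAP does not give. With the notes read as milestones, the overstatement is about 1.02 to 1.06 times for accrual over 26 to 78 weeks. Because these rates go into the submission analysis and the correction is nearly free, the wording should be settled before the interim is programmed.

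**What to change.** 1. Delete the Week 24 and Week 20 notes in Sections 10.1.2 and 10.1.3, or say that they only name scheduled milestones and do not replace actual dates.
2. State that, for participants still ongoing at the cut-off, time at risk ends at the earliest of the data cut-off date, actual last dose + 140 days, and death, whether or not an adverse event occurred.
3. Base study medication duration on actual doses up to the cut-off.
4. Apply the same rule at the Week 52 interim, where participants in safety follow-up raise the same question.
5. Reconcile these sections with Section 4.3.1, Table 4-3 and the definition of last clinical contact in Section 10.1.

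The cost is a few sentences and one revised derivation. It needs only recorded dates and the cut-off date, and nothing in trial conduct changes.

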10.1.4 Duration of exposure by COVID-19 pandemic period

- If the pandemic end date is known, then the study medication exposure duration will be calculated as follows:

$$date of last exposure date on or after pandemic start date - date of first exposure on or before pandemic end date + 28$$

- If the pandemic end date is unknown, then the study medication exposure duration will be calculated as follows:

- If the first exposure date is on or after the pandemic start date, then:
 - For study participants who did not die:

$$date of last exposure - date of first BKZ dose + 28$$

Note: If the last exposure date + 28 extends to a date beyond the final visit date (not including SFU), then this calculation reverts to:

$$date of last visit (not including SFU) - date of first BKZ dose + 1$$

- For study participants who die on or after the pandemic start date:

$$date of death - date of first BKZ dose + 1$$

- If the first exposure date is before the pandemic start date and the study drug period is overlapping with the pandemic (ie, the study participant started or ended the treatment during the pandemic) then:

- For study participants who did not die:

$$\text{date of last exposure} - 11\text{Mar}2020 + 28$$

Note: If the last exposure date + 28 extends to a date beyond the final visit date (not including SFU), then this calculation reverts to:

$$\text{date of last visit (not including SFU)} - 11\text{Mar}2020 + 1$$

- For study participants who die:

$$\text{date of death} - 11\text{Mar}2020 + 1$$

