3.2.2.2 Coronavirus Disease 2019 (COVID-19) pandemic periods

The following COVID-19 pandemic periods will be defined:

- Prior COVID-19 pandemic period: Period prior to COVID-19 pandemic start date, which is defined as 11-Mar-2020 by the World Health organization (WHO), not including the pandemic start date.
- COVID-19 pandemic period: Period from 11-Mar-2020 through the COVID-19 pandemic end date (which is currently not defined), including the dates of pandemic start and end.
- Post COVID-19 pandemic period: Period after the WHO declaration of the end of the pandemic, beginning on the day after the pandemic end date. The end of the pandemic had not yet been declared at the time of SAP finalization. As a result, this period will only be included in analyses if the WHO declares an end to the pandemic prior to the end of the study.

These periods will be used to classify the timing of the following relative to COVID-19 pandemic:

- study participant enrolment in the study,
- study participant Week 16 Visit,
- AE onset date.

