7 MEASUREMENTS OF TREATMENT COMPLIANCE

Due to the method of administration of the treatments, compliance will be examined in terms of completed injections. Treatment compliance will be calculated as:

$$\frac{\text{Total number of actual (completed) injections}}{\text{Total number of expected injections}} \times 100\%$$

The total number of expected injections is derived relative to when the study participant finishes treatment. If a study participant completes treatment, four injections are expected during the Double-Blind Treatment Period and nine during the Maintenance Period. A total of thirteen injections are then expected (at Baseline, and at each study visits from Week 4 until Week 48). If a study participant discontinues early, then the number of expected injections is based on the time of early discontinuation relative to the dosing visits.

A summary of percent treatment compliance categorized as <75% and $\geq 75\%$ will be provided by treatment group, as well as a by-study participant listing of treatment compliance.

Compliance will be summarized on the SS for the Double-Blind Period, on the MS for the Maintenance Period and on the SS for the overall period.

Injections missed due to COVID-19 will be summarized and tracked in the listings.

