10.1.5.2 Time at risk in the COVID-19 pandemic period

This period is applicable for all study participants in the SS who are still considered at risk on the 11MAR2020 (ie, those who have their first dose is on or after 11MAR2020, or for those for whom either dosing is continuing, or for whom the 140 day SFU period after last dose has not

been completed [in the case of premature treatment discontinuation or for those who do not roll over to the OLE]). The following rules will be applied:

- For study participants who started IMP prior to 11MAR2020 and did not discontinue medication in the “during COVID-19 pandemic period” (ie, for study participants with the last dose of BKZ 160mg is on or after the date of the end of the pandemic +1):

$$\text{date of the end of pandemic} - 11\text{Mar}2020 + 1$$

- For study participants who started IMP on or after 11MAR2020 and did not discontinue medication in the “during COVID-19 pandemic period” (ie, for study participants with the last dose of BKZ 160mg is on or after the date of the end of the pandemic +1):

$$\text{date of the end of pandemic} - \text{date of first dose} + 1$$

- For study participants who have died on or after 11Mar2020, and on or before the pandemic end date:

$$\text{date of death} - \text{maximum (11MAR2020, date of first dose)} + 1$$

Note: If the date of death is later than 140 days following the last dose of BKZ, this rule does not apply.

- For study participants who discontinued medication:

- in the “pre-COVID-19 pandemic period” (ie, for study participants with date of last dose of study drug before 11Mar2020), and if the earliest date between (date of last dose + 140) and (date of last clinical contact) is on or after 11Mar2020, then use minimum between:

- date of last dose + 140 – 11Mar2020 +1
 - date of last clinical contact – 11Mar2020 + 1

- in the “during COVID-19 pandemic period” (ie, for study participants with date of last dose of study drug on or after 11Mar2020, and on or before the pandemic end date),

- For study participants who started IMP prior to 11MAR2020, and if the earliest date between (date of last dose + 140) and (date of last clinical contact) is after the end of pandemic, then use:

$$\text{date of end of pandemic} - 11\text{MAR}2020 + 1$$

- For study participants who started IMP on or after 11MAR2020, and if the earliest date between (date of last dose + 140) and (date of last clinical contact) is after the end of pandemic, then use:

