$$\text{date of end of pandemic} - \text{date of first dose} + 1$$

- Else time at risk will be calculated as minimum between:

- date of last dose date + 140 – maximum (11MAR2020, date of first dose) + 1
 - date of last clinical contact – maximum (11MAR2020, date of first dose) + 1

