10.1.5.3 Time at risk in the post-COVID-19 pandemic period

This period is applicable for all study participants in the SS who are still considered at risk on the day after the end date of the pandemic (ie, those for whom either dosing is continuing or for

whom the 140 day SFU period after last dose has not been completed [in the case of premature treatment discontinuation or for those who do not roll over to the OLE)]. The following rules will be applied:

- For study participants who did not discontinue medication in the “during COVID-19 pandemic period” (ie, for study participants with date of last dose of study drug after the pandemic period end date), then use minimum between:
 - $\text{date of last dose} + 140 - \text{date of the end of pandemic}$
 - $\text{date of last clinical contact} - \text{date of the end of pandemic}$
- For study participants who have died after the *pandemic end date*:
$$\text{date of death} - \text{date of the end of pandemic}$$

Note: If the date of death is later than 140 days following the last dose of BKZ, this rule does not apply.

- For study participants who discontinued medication in the “during COVID-19 pandemic period” (ie, for study participants with date of last dose of study drug on or before the pandemic period end date), and if the earliest date between (date of last dose + 140) and (date of last clinical contact) is after the pandemic period end date, then use minimum between:
 - $\text{date of last dose} + 140 - \text{date of the end of pandemic}$
 - $\text{date of last clinical contact} - \text{date of the end of pandemic}$

To assess the impact of the COVID-19 pandemic, the study medication duration and time at risk will be reported by COVID-19 pandemic period.

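### With a known pandemic end date, the Section 10.1.4 exposure formula has its date limits on the wrong terms and returns a participant's whole exposure, not the pandemic part

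*SAP*

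**What the plan says.** SAP Section 3.2.2.2 defines the pandemic period as "Period from 11-Mar-2020 through the COVID-19 pandemic end date (which is currently not defined), including the dates of pandemic start and end". It adds that "The end of the pandemic had not yet been declared at the time of SAP finalization". A post-pandemic period enters the analyses only if an end is declared before the study ends.

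Section 10.1.4 gives two branches for study medication duration.

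- **End date known:** "date of last exposure date on or after pandemic start date - date of first exposure on or before pandemic end date + 28". Nothing is said about the final visit or death.
- **End date unknown:** a participant who started on or after 11 March 2020 is counted from the first bimekizumab dose. The other case is introduced by "If the first exposure date is before the pandemic start date and the study drug period is overlapping with the pandemic", and there the count starts at 11 March 2020. Both cases add 28 days to the last dose, revert to the last visit (safety follow-up excluded) if that visit comes sooner, and use the date of death for those who die.

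Section 10.1.5.2 sets time at risk in the same period. Its lower limit is the later of 11 March 2020 and the first dose, as in "date of last dose date + 140 – maximum (11MAR2020, date of first dose) + 1". Its upper limit is the pandemic end: "if the earliest date between (date of last dose + 140) and (date of last clinical contact) is after the end of pandemic, then use" the end date.

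Section 10.1.5.3 closes with the requirement that "the study medication duration and time at risk will be reported by COVID-19 pandemic period".

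**The concern.** Exposure inside a window is limited below by the window's start and above by its end. The known-end formula pairs them the other way round. A last dose required to fall on or after the start is simply the participant's last dose, and a first dose required to fall on or before the end is simply the first dose. Exposure before 11 March 2020 and after the end date is therefore counted as pandemic exposure.

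Reading the two phrases as conditions for entering the calculation changes nothing. They then select participants who overlap the pandemic, and the subtraction still gives whole exposure.

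At stake is the by-period exposure summary that Sections 3.11 and 10.1.5.3 call for. Programmed literally, pandemic duration would equal total duration for every participant who crosses a boundary. Section 10.1.4 also has no duration formula for the pre-pandemic or post-pandemic period, so nothing else in it separates the periods.

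**Working it through.** The SAP states no numerical result for this formula, so there is no figure to reproduce. The check applies each rule to the same dosing dates.

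**Inputs**
- Pandemic start: 11 March 2020 (Section 3.2.2.2).
- Dosing: 13 injections from Baseline to Week 48 (Section 7), 28 days apart, all bimekizumab. The span from first to last dose is 12 × 28 = 336 days.
- Final visit: assumed to be on schedule, 28 days after the last dose, so the last-visit rule does not shorten the count.
- Pandemic end date E: not in the SAP. Example 1 needs only that E falls after the participant's exposure ends. Example 2 is written relative to E.

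**Example 1: treatment starts before the pandemic.** First dose 2 September 2019; last dose 336 days later, 3 August 2020.
- Known-end branch: 336 + 28 = **364 days**.
- Unknown-end branch: 11 March to 3 August 2020 is 145 days, and 145 + 28 = **173 days**.
- Difference: 364 − 173 = 191 days, or 191/173 = 110% of the correct value. This is exactly the pre-pandemic exposure, 2 September 2019 to 10 March 2020.

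This participant's exposure ends on 30 August 2020 (last dose + 27). Learning a later end date should change nothing, yet it moves the result from 173 to 364. The SAP rests on Protocol Amendment 4 of 16 February 2021 (Section 1) and says that no end had been declared at finalization, so E cannot be as early as August 2020.

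**Example 2: treatment continues past the end.** First dose E − 150; last dose E − 150 + 336 = E + 186.
- Known-end branch: 336 + 28 = **364 days**.
- Clipped at E: E − (E − 150) + 1 = **151 days**.
- Difference: 364 − 151 = 213 days, all post-pandemic.

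**Wholly inside the period.** With first dose on 1 April 2020 and last dose on 3 March 2021, and E after the end of exposure, both methods give 364 days, so there is no error.

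**Is it enough to exchange the two limits?** No.
- In Example 1 the first dose on or after 11 March 2020 falls on 16 March. 3 August − 16 March = 140, and 140 + 28 = 168, against 173. The days 11 to 15 March, covered by the 17 February dose, are lost.
- In Example 2 the last dose on or before E is at E − 10. (E − 10) − (E − 150) + 28 = 168, against 151. The added 28 days run past the pandemic end.

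**The case against.** The strongest reply is that the branch is dormant. No end had been declared when the SAP was finalized, and until one is, the unknown-end branch applies and cuts correctly at the start. That stands as a limit on the consequence. It does not remove the error, because the SAP provides for a declared end.

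A reader might infer that by-period adverse event rates are distorted, or that exposure would cease to agree with the time at risk behind them. The SAP does not support this. Section 10.2.4 takes the denominators of the by-period EAIR and EAER from Section 10.1.5, which is clipped. The two quantities also differ by design: duration adds 28 days to the last dose, and time at risk can run to 140 days.

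A reader might also take 110% as the error in the table. It describes one constructed participant. The SAP gives no enrolment dates, so the number of boundary-crossing participants is unknown.

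The missing final-visit and death rules, and the missing pre- and post-pandemic formulas, are separate omissions from the misplaced limits. They belong here only because the same rewrite settles them.

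**Conclusion.** The known-end formula is wrong as written. It contradicts the other branch of Section 10.1.4 and the two-sided clipping in Section 10.1.5.2, and no other part of the SAP corrects it. In the examples it overstates pandemic exposure by 191 days (364 against 173) and 213 days (364 against 151). Participants whose exposure lies wholly inside the period are unaffected, unless a final-visit or death rule should have changed their count.

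This is a minor correction. It matters only if an end date is declared before an analysis, and only for the descriptive by-period exposure summary. By-period EAIR and EAER and all efficacy analyses are unaffected. The day counts assume 28-day dosing, bimekizumab throughout and an on-schedule final visit. They do not depend on a particular end date, beyond its falling after exposure ends in Example 1.

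**What to change.** Define one exposure end date by the SAP's existing rules: the date of death for those who die; otherwise the earlier of last dose + 27 and the last visit excluding safety follow-up. Then, for participants whose exposure interval overlaps the period (otherwise 0 days):

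- **Pandemic:** min(exposure end date, pandemic end date) − max(first BKZ dose, 11 March 2020) + 1.
- **Pre-pandemic:** min(exposure end date, 10 March 2020) − first BKZ dose + 1.
- **Post-pandemic:** exposure end date − max(first BKZ dose, pandemic end date + 1) + 1.

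In Example 1 this gives 191 pre-pandemic and 173 pandemic days, total 364. In Example 2 it gives 151 pandemic and 213 post-pandemic days, total 364.

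The overlap condition is needed. Without it, a last dose on 1 January 2020 (exposure end 28 January 2020) would give −43 + 1 = −42 pandemic days.

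The three periods add up to bimekizumab exposure computed with this same exposure end date. They should not be described as summing to every total in Section 10.1, because placebo exposure of participants who later switch is not included.

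The cost is one clipped expression with three sets of limits in Section 10.1.4 and the matching derivation in the exposure dataset. No new data are needed.
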